3.2 Secondary outcomes

We will analyze secondary outcomes however due to sample size will not be able to power differences in pregnancy rate and live birth rate. Descriptive secondary outcomes will include positive pregnancy test, clinical pregnancy, and ongoing pregnancy. We will also evaluate number and size of developing follicles determined by ultrasound, endometrial thickness and pattern by ultrasound. We will also monitor adverse events during treatment and side effect profile of both treatment arms.

We will evaluate pregnancy outcomes and report any fetal anomalies.

4 STUDY DESIGN

Treatment Design: This will be a single center, open trial of oral letrozole vs. combination of oral letrozole and clomiphene citrate in the treatment of infertility in patients with polycystic ovary syndrome. Patients will be randomized to receive either a dose of 2.5 mg of letrozole or 2.5mg of letrozole and 50 mg of CC for 5 days on cycle days 3 through 7 of the menstrual cycle. Patients will be monitored during the cycle with a mid-cycle ultrasound (cycle days 12-14) and a mid-luteal progesterone level (cycle day 21).

The study will last for -1 cycles or approximately -5 weeks.

Randomization will be stratified by age (< 35 versus \geq 35) and BMI (< 30 and \geq 30) to ensure equal groups to study. Randomization will be via a computer based central randomization to ensure adequate allocation concealment.

Enrollment will take approximately 18 months if ~ 3.89subjects are enrolled per month. Active subject participation will be through completion of -1 cycle. We will follow up with patient regarding pregnancy, delivery outcomes, and if information is not available via chart abstraction.

4.1 Study Summary

Initial visit:

- 1. Study staff review pre-screening questionnaire and confirm eligibility criteria
- 2. Obtain signed informed consent
- 3. Confirm documentation of vital signs, height, weight and BMI.
- 4. Record and review medical history
- 5. Request subject to sign medical release form to obtain information regarding ongoing infertility treatment, pregnancy and delivery information.
- 6. Complete urine pregnancy test or dispense urine pregnancy test to complete at a later date if participant plans on delaying treatment.
 - 7. Randomization to treatment group once negative pregnancy test.

- Orient and dispense calendar log which includes documentation of intercourse, menstrual log and side effect assessment
 - Dispense study medications

Mid-cycle Visit (Visit #2):

- 1. Collect journal logs
- 2. Transvaginal ultrasound exam
- 3. Return medication containers and study medications you did not take
- 4. Dispense urine pregnancy test

Mid-luteal lab draw (visit #3)

- 1. Blood draw (P4)
- 2. Schedule End of treatment visit

End of Treatment Visit:

- 1. Collect Calendar log
- 2. If subject had a positive urine pregnancy test: blood draw will be performed and then repeated approximately 48 hours after the first one.
 - 3. Complete End of Treatment questionnaire
- 4. Arrange for follow up and confirm we have a release of records for pregnancy and neonatal records.

4.2 Study Population:

70 women with PCOS actively seeking pregnancy (or 35 per each treatment arm) aged \geq 18 to \leq 40 years will be enrolled. The overall goal of enrollment criteria is to identify a population of healthy women with PCOS and infertility not specified by another cause. Infertility will be determined by clinical history. PCOS will be determined by Rotterdam criteria which includes two of three findings: oligo- or anovulation, hyperandrogenism or polycystic ovaries on ultrasound.

- Hyperandrogenism will be determined by evidence of hirsutism on exam or by biochemical elevations in total testosterone.
- Ultrasound findings of polycystic ovaries including ≥ 12 follicles of 2-9 mm diameter or increased ovarian volume (>10 cm³) in either ovary.

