Clomiphene citrate (CC) is a commonly used pharmacologic agent to induce ovulation in women with PCOS. It works as a selective estrogen receptor modulator (SERM) by competitively attaching to nuclear estrogen receptors. As the negative feedback of estrogen is lowered it in turn activates increased secretion of gonadotropin hormones which subsequently causes ovarian follicular growth. CC also has an antiestrogenic effect on endometrial development and cervical mucus production. This has been implicated to contribute to the low pregnancy rate despite a relatively high ovulation rate. ^{2, 3} Letrozole has a different mechanism of action and works as a highly selective aromatase inhibitor thus preventing androgen-to-estrogen conversion. The negative feedback in the hypothalamus is decreased by the suppressed estrogen production which subsequently increases the concentration of follicle stimulating hormone (FSH). An additional mechanism of aromatase inhibitors may result from increase follicular sensitivity to FSH resulting from temporary increased intraovarian androgens. 4 Studies in primates have shown that testosterone augments follicular FSH receptor expression which supports the idea that androgens promote follicular growth. 5-7 Additionally, Garcia-Velasco et al demonstrated an increase in intraovarian androgen concentrations with the use of letrozole in low responder patients undergoing IVF.8 Letrozole offers a benefit over CC for ovulation induction since it does not deplete estrogen receptors in both central and peripheral target tissues and normal central feedback mechanisms remain intact. Recently, a randomized control trial comparing letrozole to clomiphene demonstrated that letrozole was associated with higher live-birth rate (27.5% vs 19.1%, P=0.007, 95% CI 1.10 to 1.87) and cumulative ovulation rate (61.7% vs. 48.3%, P<0.001) among women with polycystic ovary syndrome. 9 Despite the superior ovulatory and live birth rates with letrozole compared to CC the question remains if there are medical alternatives without proceeding to gonadotropins or IVF both of which are associated with increased costs and risks.

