2.2 Rationale

Letrozole has been shown to have both higher live-birth and ovulation rates compared to CC among infertile PCOS women demonstrated by the PPCOS II trial. Despite the superior ovulatory and live birth rates with letrozole compared to CC the question remains if there are medical alternatives without proceeding to gonadotropins or IVF both of which are associated with increased costs and risks. One study has shown a potential benefit in combining letrozole and CC however a double blind trial is needed to test if this combination improves outcomes over letrozole alone.

Mechanistically, the combination may have a synergistic action with letrozole having a local effect at the level of the ovary to block estrogen synthesis and with clomiphene having a central effect by antagonizing the negative feedback of estrogen at the hypothalamus by depleting estrogen receptors. These different mechanisms of actions may provide a synergistic effect to provide improved ovulation rates over use of letrozole alone. Since the combination of letrozole and clomiphene has not yet been studied in a prospective randomized fashion and it is unclear if this will offer an advantage over letrozole alone in terms of both ovulation and pregnancy rate, we have designed a pilot study to characterize the ovulatory rate with this combination treatment. It is necessary to first determine if the combination treatment is at least equivalent and possibly better than the standard efficacy of letrozole. Prior to embarking on a larger trial to look at the most important outcome of live birth rate it is important to establish that this combination treatment does offer a superior ovulatory rate. The aim of this study is to test the hypothesis that combined therapy of letrozole and CC is an effective and superior method to letrozole alone to achieve ovulation in women with PCOS.

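### The mid-cycle scan supplies four reader-dependent secondary outcomes in an open trial, and the plan does not say that the person reading it is kept unaware of the arm

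*Combined protocol and SAP*

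**What the plan says.** Section 4 states the design: "This will be a single center, open trial of oral letrozole vs. combination of oral letrozole and clomiphene citrate". The safeguard it describes concerns assignment: "Randomization will be via a computer based central randomization to ensure adequate allocation concealment".

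Section 3.2 makes the scan measures secondary outcomes: "We will also evaluate number and size of developing follicles determined by ultrasound, endometrial thickness and pattern by ultrasound". The Précis in the Protocol Summary adds that the follicles counted are those above 15 mm.

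Section 4.1 numbers the steps of Visit #2. Journal logs are collected first. The scan is second, given only as "Transvaginal ultrasound exam". The third step is "Return medication containers and study medications you did not take". The only log whose content the plan describes is the calendar log handed out at the initial visit, in which the participant notes intercourse, bleeding and side effects.

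The text available for review names no scan reader and contains no reading procedure, stored images, central reading or masking of the reader.

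**The concern.** Caliper placement, a count against a fixed 15 mm cut and a pattern category all leave room for judgement. A reader who knows the arm can, without intending to, resolve doubtful cases differently in the two arms. For the endometrium the plan itself supplies a possible expectation, since Section 2.1 says that "CC also has an antiestrogenic effect on endometrial development and cervical mucus production".

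At stake is how far the randomized comparison of follicular and endometrial response can be trusted. Section 2.3.1 says the multiple pregnancy rate of the combination is unknown, and Section 3.2 says the study is not powered for pregnancy or live birth. Readers will therefore look to the scan for information on how the combination acts. Bias in a live reading is hard to undo afterwards, particularly when no image storage is described.

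**Working it through.** **Group size.** The point rests on no figure stated in the plan, but the illustrations below use its group size, so that was reproduced first. Section 6.1.4 gives 0.50 versus 0.83, two-sided 5%, 80% power.

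- n = [1.960·√(2·0.665·0.335) + 0.842·√(0.50·0.50 + 0.83·0.17)]² / 0.33² = (1.308 + 0.526)² / 0.1089 = 30.9, so 31 per arm (power 80.1%).
- With 10% dropout: 31 / 0.90 = 34.4, so 35 per arm. Both figures agree with the plan.

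**Passages set side by side.**

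| Question | What the documents show |
|---|---|
| Is treatment open? | Yes (Précis; Section 4) |
| Is outcome reading protected? | Nothing stated; only assignment is concealed (Section 4) |
| Are the scan outcomes compared between arms? | Yes, as secondary outcomes (Protocol Summary, Objectives; Section 3.2) |
| Will the reader know the arm? | Not stated |
| What could reveal it before the scan? | The participant, who knows her treatment, and possibly the logs, which are listed first |
| Does the scan time the primary blood draw? | No; the draw follows a reported LH surge or a fixed cycle day (Section 3.1.1) |
| Does the scan drive treatment? | No such rule found |

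The last two rows mean that nothing found in the plan requires the reader to know the arm.

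**Illustration for a proportion.** The documents give no rate of borderline scans, so two to four per arm is an assumption.

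- One woman reclassified: 1/35 = 2.9 points. Two: 2/35 = 5.7 points. Four: 4/35 = 11.4 points. These require every borderline case in the arm to be moved the same way.
- If the other arm shifted equally in the opposite direction, the difference would move by 2 × 5.7 = 11.4 to 2 × 11.4 = 22.9 points.
- For scale, near a proportion of 0.5 the standard error of the difference is √(2·0.25/35) = 0.120, or 12 points, with a 95% half-width of 1.96 × 12.0 = about 23 points.

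**Illustration for a continuous measure** (follicle size, endometrial thickness). The documents give no standard deviation, so the shift b is in SD units and assumed. The standard error of a mean difference is √(2/35) = 0.239 SD. With no true effect, the chance of a nominally significant result is 1 − Φ(1.96 − b/0.239) + Φ(−1.96 − b/0.239).

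| Assumed shift b (SD) | b / 0.239 | False-positive rate, 35 per arm | Same, 31 per arm |
|---|---|---|---|
| 0.1 | 0.42 | 7.0% | 6.8% |
| 0.2 | 0.84 | 13.3% | 12.3% |
| 0.3 | 1.26 | 24.1% | 21.9% |
| 0.5 | 2.09 | 55.2% | 50.3% |

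Section 6.1.3 specifies tests for ovulation only, so this table also assumes a significance test that the plan does not specify for the scan measures.

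**The case against.** The strongest reply is that silence is not unmasking: the plan never says that the reader will know the arm, the outcomes are secondary in a pilot, and the size of any bias is wholly assumed. All of that stands. It limits the point to a missing safeguard.

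Several stronger readings are tempting, and the documents do not support them.

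- A reader might infer that the returned containers show the arm to the person scanning. Section 4.1 lists their return after the scan; only the logs come before it.
- A reader might infer that the scan decides whether the larger trial goes ahead. Section 2.2 makes that depend on a superior ovulation rate, which is the progesterone outcome.
- A reader might infer that the plan leads the scan reader to expect more follicles with the combination. Section 2.2 postulates synergy for ovulation and predicts no follicle count. The endometrial statement in Section 2.1 has a textual basis but does not say that the lining will be thinner.
- A reader might take the scan to be the sole source on multifollicular response. The Protocol Summary also reports the multiple pregnancy rate, though events will be sparse with 35 women per arm.
- Section 2.2 says "however a double blind trial is needed to test if this combination improves outcomes over letrozole alone". That conflicts with the open design, but it concerns the trial as a whole. Masking the scan reader would not make the trial double blind, and the point here does not depend on that sentence.

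A further reply is that masking may not be free. The plan does not describe staffing and names both the Women's Health Clinic and the Quad Cities clinic. If the person scanning also randomizes or dispenses, tasks would have to be divided. That stands as a cost. It does not remove the benefit, since no use of the scan found in the plan requires knowledge of the arm.

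**Conclusion.** The point holds as a low-cost improvement confined to the four secondary scan outcomes. The design is open, the measurements depend on the reader, and no masking of the reader is stated. The bias is of unknown size and direction. The shift of 5.7 to 11.4 points in one arm and the false-positive rates of about 7% to 55% show only what the assumed inputs would produce. Even the largest one-arm shift, 11.4 points, lies within one standard error (12 points) of the difference between arms.

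A reader might go further and infer that the trial's main result is at risk. The documents do not support this: the primary outcome is a laboratory progesterone value, and the scan does not set the time of its blood draw.

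**What to change.** In Section 4.1, Visit #2, state that:

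- the person who performs and reads the scan is not told the treatment arm, and the scan request carries study ID only;
- follicle and endometrial measurements are recorded before the logs are collected or reviewed, which moves the logs from first place in the list, and before containers are returned, as the list already has it;
- participants are asked not to mention their treatment to the reader, and any disclosure is recorded.

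This needs no added visit, procedure or participants, and leaves 35 per arm and the power for the primary outcome as they are. Masking will be imperfect because participants know their arm; the record of disclosures shows how often it failed. Where the scanner also randomizes or dispenses, existing staff must split those tasks. If a clinic cannot do that, the scan comparisons should be reported as unmasked.

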5 STUDY ENROLLMENT AND WITHDRAWAL

5.1 Subject Inclusion Criteria

In order to be eligible to participate in this study, the participant must meet all following criteria:

- 1. Provide signed and dated informed consent.
- 2. Willing to comply with all study procedure and be available for the duration of the study. Ability to have regular intercourse during the ovulation induction phase of the study.
- 3. Diagnosis of infertility: Inability of couple to achieve successful pregnancy after 12 months of regular timed unprotected intercourse in women less than 35 years of age; and after 6 months of regular intercourse without use of contraception in women 35 years and older.¹¹ If in the clinical case of anovulation, 12 month period of time "infertility" is not necessary.
- 4. Diagnosis of polycystic ovary syndrome: based on Revised Rotterdam criteria which includes two of the three following findings¹² and the definitions and criteria are modified from the PPCOS II trial⁹:
- 1. Oligomenorrhea or chronic anovulation: spontaneous intermenstrual periods of \geq 45 days or a total of \leq 8 menses per year. In women with more regular bleeding patterns but suspected anovulatory bleeding, a mid-luteal serum progesterone level < 3 ng/mL is consistent with chronic anovulation. For women with a history of \leq 8 menses per year however now have regular menses due to initiation of insulin sensitizing agents or active weight loss efforts within the last year prior to the study would qualify as evidence of oligomenorrhea.
- 2. Hyperandrogenism (clinical or biochemical): clinical hyperandrogenism demonstrated by hirsutism and biochemical hyperandrogenism demonstrated by hyperandrogenemia. Hyperandrogenemia defined as an elevated total testosterone based on the laboratory criteria. Labs could be local or from UIHC.
- 3. Polycystic ovaries on ultrasound: defined as either an ovary that contains 12 or more follicles measuring 2-9 mm in diameter, or an increased ovarian volume (>10 cm³) on one ovary.
- 5. Normal sperm concentration of 15 million/mL and with normal motility of > 40% according to World Health Organization cutoff points, in at least one ejaculate during the previous year.¹³ Morphology results will not affect eligibility. If male partner has fathered a child, SFA is not necessary.

5.2 Subject Exclusion Criteria

- 1. Current pregnancy. Patient will take a urine pregnancy test prior to starting treatment medication.
- 2. Patients currently taking hormonal contraception. A 1 month washout for any type of combined contraceptive or oral progestins will be required. If use of hormonal implants or depo progestins a longer washout of 3 months will be required.
- 3. Patients with other known cause of infertility: endometriosis, tubal factor, uterine abnormalities.
- 4. Patients with uncorrected thyroid disease defined based on their local lab or at UIHC (0.27 to 4.20 μ IU/mL). Once corrected and within this range, they may be enrolled if the other inclusion and exclusion criteria are met. A normal lab within the last year is adequate for entry.
- 5. Patients with untreated hyperprolactinemia. A normal prolactin within the past year at local lab or at UIHC (4.8 to 23.3 ng/mL) is adequate for entry.
- 6. Medical conditions in which we recommend avoiding pregnancy until under improved control:
- -Patients with poorly controlled Type 1 or Type 2 diabetes (defined as a hemoglobin A1c > 6.5%)
- Patients with poorly controlled hypertension (defined as systolic blood pressure ≥ 160 mm Hg or diastolic ≥ 100 mm Hg on two measures at least 60 minutes apart)
- 7. Patients with contraindications to clomiphene citrate: hypersensitivity to CC or any of its components, history of liver disease or known liver disease (LFT's are not necessary prior CC use and enrollment into the study), unknown cause of abnormal uterine bleeding, intracranial lesion.
- 8. Patients with contraindications to letrozole: hypersensitivity to letrozole or any of its components.
- 9. Patients taking medications known to affect reproductive function or metabolism or that are an absolute contraindication during pregnancy.
- 10. If patients are suspected based on clinical findings for other etiologies that mimic PCOS, work up must be completed to exclude other etiologies prior to enrollment (i.e. Cushing's syndrome, androgen-secreting tumor).

6 STATISTICAL CONSIDERATIONS

6.1 Justification of effect size

6.1.1 Prior Studies

The primary outcome is ovulation, defined by a mid-luteal progesterone level > 3 ng/mL. There is data demonstrating the cumulative live birth rate with clomiphene and letrozole from the PPCOS II trial. This trial compared letrozole to clomiphene demonstrated that letrozole was associated with a higher cumulative ovulation rate (61.7% vs. 48.3%, P<0.001) among women with polycystic ovary syndrome and the rate of ovulation after one treatment cycle with letrozole 2.5 mg was 50%.9 Unfortunately, there is no comparative quality data from randomized trials of the combination of letrozole and CC. There is one study that prospectively reviewed treatment outcomes using a combination of letrozole and clomiphene who had previously failed CC for 6 cycles and letrozole for 4 cycles. This study enrolled 100 patients and showed an ovulatory rate (defined by development of dominant follicle) of 82.9% of cycles (213/257) with the combination treatment. 10 However, this study was not randomized and used a limited population of women with PCOS that were resistant to both clomiphene and letrozole alone. Additionally, patients received Gonal-f on day 11 if a dominant follicle was present and then received hCG trigger when the follicle was >18 mm in size followed by IUI 36-38 hours later.

6.1.2 Minimum Clinically Important Difference

Since this is a pilot study our goal is to balance the risk of avoiding a type 2 error and having an attainable sample size. We have set a benchmark of 30% difference between groups as a clinically meaningful.

6.1.3 Significance Testing

Primary statistical analyses will invoke the intent-to-treat approach. Primary efficacy analysis will be performed by comparing the treatment groups with respect to the primary outcome of ovulation using Pearson chi-square test. Additional analysis will be performed using logistic regression model to adjust for other factors such as the randomization stratification of age and BMI and prior exposure to study medications. A per protocol analysis will also be performed.

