3.1.1 Primary Outcome measures

The primary outcome measure is the occurrence of ovulation defined as a mid-luteal progesterone level > 3 ng/mL. This will be tested 7 days following the patient reporting of an LH surge. If no LH surge is detected the lab will be drawn on cycle day 21 or 22. The primary analysis of ovulation rate within the two treatment conditions will employ an intent-to-treat approach.

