6.1.4 Sample Size calculations

A sample size of 31 subjects in each arm of the randomization yields 80% statistical power to prospectively demonstrate a 0.30 absolute difference in ovulation rate between treatment arms (0.50 for Letrozole and 0.83 for combined letrozole and CC) using the Pearson's chi-square test having a two-sided significance level of 0.05. The sample size has been inflated to 35/arm to allow for a dropout rate of 10%. Dropout rate in the PPCOS II trial was 19.5% in the letrozole group however this was a longer study in

which they did 5 cycles and also a more involved study than the one we are proposing. Since there are fewer visits, fewer surveys and shorter enrollment period we anticipate a lower dropout rate in this trial.

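### Does the intent-to-treat primary analysis need a written rule for randomised women who have no progesterone result?

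*Combined protocol and SAP*

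**What the plan says.** Section 3.1.1 fixes the endpoint: "The primary outcome measure is the occurrence of ovulation defined as a mid-luteal progesterone level > 3 ng/mL". It continues: "The primary analysis of ovulation rate within the two treatment conditions will employ an intent-to-treat approach". The Précis in the Protocol Summary also calls the primary analysis intent-to-treat, as does Section 6.1.3: "Primary statistical analyses will invoke the intent-to-treat approach". Section 6.1.3 names the Pearson chi-square test, a logistic regression adjusted for the stratification factors and prior exposure, and one further analysis: "A per protocol analysis will also be performed".

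Section 4.1 places randomisation at the initial visit ("Randomization to treatment group once negative pregnancy test") and the P4 draw at the third visit. A woman can therefore be randomised and never have the endpoint measured. Section 3.1.1 has a fallback for the day of the draw when no LH surge is detected, but none for a result that does not exist.

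Section 6.1.4 states 80% power with 31 women per arm at 0.50 versus 0.83, two-sided 0.05. It adds "The sample size has been inflated to 35/arm to allow for a dropout rate of 10" percent. For comparison it reports "Dropout rate in the PPCOS II trial was 19.5% in the letrozole group", and explains that the earlier trial was longer and more demanding.

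**The concern.** The label intent-to-treat does not by itself say what to do with a missing outcome, and the plan can be read two ways. Analysing everyone as randomised suggests a denominator of 35 per arm, with a woman lacking P4 counted as not having met the definition. Inflating 31 to 35 suggests instead that dropouts leave the denominator and about 31 per arm are tested. The per-protocol analysis is not defined, so it does not settle the matter.

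In a trial this small, three or four women per arm can move a p-value across 0.05. The trial is open, so the rule could in principle be chosen after the results are known. Section 2.2 makes a superior ovulation rate the condition for a larger live-birth trial, so the verdict on the primary test has consequences. The planned 80% also holds under one reading and not, in general, under the other.

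**Working it through.** **Inputs.** From Section 6.1.4: rates 0.50 and 0.83, two-sided 0.05, 31 per arm inflated to 35, 10% dropout, and 19.5% in the earlier trial's letrozole group. From Section 6.1.3: Pearson chi-square, taken without continuity correction. *Assumptions not in the documents:* every dropout lacks P4; unless stated otherwise, each woman is lost independently, at the same rate in both arms, and regardless of ovulation.

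**1. The plan's own figure.** Power ≈ Φ{[Δ − 1.96·√(2p̄(1−p̄)/n)] / √[(p₁(1−p₁)+p₂(1−p₂))/n]}.

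With n = 31, Δ = 0.33, p̄ = 0.665: (0.33 − 1.96 × 0.1199)/0.1123 = 0.846, so power is 80.1%. Inflation: 31/0.9 = 34.4, rounded up to 35. Both stated numbers reproduce.

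**2. Missing counted as not ovulating.** The rates become 0.50 × 0.9 = 0.45 and 0.83 × 0.9 = 0.747, with n = 35, Δ = 0.297, p̄ = 0.5985: (0.297 − 1.96 × 0.1172)/0.1117 = 0.603, so power is 72.7%. If instead all the missing women are non-ovulators, this rule leaves the rates at 0.50 and 0.83, and power at n = 35 is 84.8%.

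**3. Both rules on the same data.** Exact enumeration over the binomial number observed in each arm and the binomial number ovulating among them, applying the test under each rule (0.50 vs 0.83, 35 per arm):

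| Loss, letrozole / combination | Power, P4 only | Power, missing = not ovulating | Opposite verdicts |
|---|---|---|---|
| 5% / 5% | 83.9% | 79.6% | 7.9% |
| 10% / 10% | 81.8% | 72.5% | 13.3% |
| 19.5% / 19.5% | 77.0% | 59.1% | 22.2% |
| 5% / 15% | 81.5% | 49.5% | 32.3% |
| 15% / 5% | 81.8% | 89.2% | 9.9% |

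With fixed losses near 10%, opposite verdicts occur in 5.5% of trials (3 and 3 women), 7.8% (4 and 4), 13.8% (3 letrozole, 4 combination) and 1.7% (4 letrozole, 3 combination). At 10% random loss, 11.30 of the 13.35 points (85%) are significant only with P4 alone. With 15% / 5% loss the direction reverses: 8.7 of 9.9 points are significant only when missing counts as not ovulating. If the 10% missing are all non-ovulators (simulation, 2 million trials), disagreement is 10.3%.

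**4. No true difference (0.50 in both arms).** At 10% equal loss, false positives are 5.2% with P4 only and 4.4% with missing as not ovulating. Reporting whichever is significant gives 6.2% (6.9% at 19.5% loss). At 5% versus 15% loss, P4 only stays at 5.2%, while missing as not ovulating rises to 6.3%.

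**5. Worked tables, 4 missing per arm.** 16/31 vs 24/31: p = 0.034; 16/35 vs 24/35: p = 0.053. The combination rate here is 24/31 = 0.77, below plan. Near the planned rates both readings are significant: 16/31 vs 26/31, p = 0.007; 16/35 vs 26/35, p = 0.015.

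**The case for a change.** The strongest case for a change is that one sentence would close the gap at no cost in patients or visits, and that leaving it open lets the result influence the rule. Disagreement in roughly one trial in eight is not negligible. The 80% in Section 6.1.4 does depend on dropouts leaving the denominator, unless those who drop out are mainly non-ovulators.

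What stands is that no section supplies the rule, and that the figures above are correct under their assumptions. Three things weaken the case for a change.

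- The one-in-eight figure belongs to one loss pattern that the plan does not specify. It is not a property of the design.
- The gain from choosing the favourable rule under equal 10% loss is about one percentage point of false positives (6.2% against 5.2%), and it assumes deliberate selection. It would be larger with unequal loss, where counting missing as failure already gives 6.3% by itself. The endpoint is a laboratory value, so the open label adds little beyond that.
- The remedy that seems most natural, counting missing as not ovulating, does not follow from the text. Section 3.1.1 defines ovulation by a measured value and does not say that an undrawn sample means no ovulation. That rule would also count as a failure a woman who conceived in the study cycle but had no P4 drawn.

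**Conclusion.** No change follows. The plan omits a detail that analysts commonly fill, and both ordinary ways of filling it are defensible. Leaving out women without P4 keeps close to the planned power and, if loss is unrelated to ovulation, keeps the false-positive rate near 5% even when loss differs by arm. Counting them as not ovulating keeps every randomised woman in the denominator and preserves the true rates if those lost are non-ovulators. Its costs are power of about 73% under equal random loss, about 50% under 5% versus 15% loss at the planned rates, and 6.3% false positives under that imbalance. Neither rule is better across these cases, so prescribing one would exchange one set of weaknesses for another.

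No stated figure is wrong: 31 per arm, 35 per arm and 80% all reproduce. The trial is a one-cycle pilot (Sections 2.2 and 6.1.2) expecting about 0.10 × 35 = 3.5 losses per arm, and near its planned rates with four lost per arm both readings are significant. Once ovulating, not ovulating and missing are reported by arm, as is ordinary practice, a reader can compute either test. The size of the issue is a 13% chance of opposite verdicts at 10% equal random loss, within a range of about 2% to 32% for splits around 10%. All of this assumes that every dropout lacks P4, that loss is unrelated to ovulation, and that the chi-square test is uncorrected.
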